4) Serum thromboxane B2: The concentration of serum thromboxane B2 (TXB2) will be measured by using the TXB2 EIA kit (Cayman Chemical Company, Ann Arbor, MI) according to the instructions of the manufacturer, as previously described [24]. Briefly, samples will be diluted with EIA buffer to bring their concentrations within the range of the standard curve. No other purification will be performed on any of the samples. A standard curve will be established by serial dilution of TXB2 between 1000 pg/mL and 7.8 pg/mL using EIA buffer as the matrix. The concentration of TXB2 in the samples will be calculated from a logistic 4-parameter fit of the standard concentrations versus percentage bound/maximum bound.

Study endpoints and sample size calculation

The primary end point of our study is the comparison of CAT-induced MPA between DAPT and DAPT plus vorapaxar after 30 ± 3 days of treatment. We hypothesize that adjunctive vorapaxar will result into a significant reduction of platelet aggregation. Assuming a 10% absolute reduction in CAT-induced MPA with a common standard deviation of 13%, 37 patients per group will be needed to detect a significant difference between DAPT and DAPT plus vorapaxar with a 90% power and 2-sided $\alpha=0.05$. Considering a possible 30-35% rate of invalid results due to hemolysis or drop-out and the three arms of treatment up to 146 patients will need to be randomized. Since there are no preliminary data in this particular setting, the sample size of our study was calculated based on previous data of vorapaxar in addition to DAPT with aspirin and clopidogrel [21]. This approach is in agreement with recommendations for pilot investigations [25].

Our secondary outcome will be the comparison of CAT-induced MPA between vorapaxar in addition to a new generation P2Y₁₂ receptor inhibitor (prasugrel or ticagrelor) and vorapaxar in addition to standard DAPT (aspirin and prasugrel/ticagrelor). We hypothesize that stopping aspirin will not lead to significant differences in CAT-induced MPA after 30 ± 3 days of treatment.

Other objectives will include the comparisons among the 3 groups of all PD parameters measured by multiple assays at every time point, as well as intragroup comparisons of PD parameters in order to evaluate the variability over time of vorapaxar PD effects, as well as how PD measures will be affected by aspirin withdrawal.

Statistical analysis plan

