Categorical variables will be expressed as frequencies and percentages. Continuous variables will be presented as mean \pm SD or median [IQR]. Continuous variables will be analyzed for normal distribution with the Kolmogorov-Smirnov test. Comparisons between categorical variables will be performed using two-tailed Fisher's exact test or the Pearson's chi-square test. Student's t test, Mann-Whitney U-test and Wilcoxon test will be used to compare continuous variables when appropriate. An analysis of covariance (ANCOVA) method with a general linear model, using baseline variables significantly different between groups as covariates, will be used to evaluate the overall difference between groups and all between-groups comparisons, in line with other PD studies [23]. Analysis of variance (ANOVA) will be used to evaluate intragroup comparisons. A 2-tailed p value of < 0.05 is considered to indicate a statistically significant difference for all the analyses performed. Statistical analysis will be performed by our group using SPSS v22.0 software (SPSS Inc. Chicago, IL).

Publication Strategy/Additional Information

Study subjects will be identified first (months 1-24): we expect to enroll approximately 5-6 subjects monthly and complete enrollment in 24 months (total: 126 subjects enrolled). Months 25-26 will be implied for statistical analysis and months 27-28 for manuscript preparation. We intend to present data at a major scientific meeting at completion of the study.

We anticipate no major problems with the described protocol since the approach is a straight forward prospective study and is based on well-established methods. However, since there is limited experience with vorapaxar to define platelet function, variability may be higher than expected and we cannot currently perform a detailed sample size calculation. We anticipate adding this to the protocol after inclusion of the study population has been completed. If the sample size after one year is estimated to be too small, additional patients will be included. This approach is in agreement with recommendations for pilot investigations [25].

Possible Discomforts and Risk

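### The plan gives two different totals (up to 146 randomised, 126 enrolled), and at its own 30-35% loss neither leaves the 37 evaluable patients per arm needed for the stated 90% power

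*Combined protocol and SAP*

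**What the plan says.** Under *Study endpoints and sample size calculation*, the primary comparison is defined as follows: "The primary end point of our study is the comparison of CAT-induced MPA between DAPT and DAPT plus vorapaxar", at 30 days. The inputs are "Assuming a 10% absolute reduction in CAT-induced MPA" "with a common standard deviation of 13" percentage points, with two-sided alpha 0.05. The result is "37 patients per group will be needed to detect a significant difference between DAPT and DAPT plus vorapaxar with a 90% power". The same paragraph then moves from evaluable to randomised patients: "Considering a possible 30-35% rate of invalid results due to hemolysis or drop-out and the three arms of treatment up to 146 patients" are to be randomised.

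Under *Publication Strategy/Additional Information* a different total appears: "we expect to enroll approximately 5-6 subjects monthly and complete enrollment in 24 months (total: 126 subjects enrolled"). That section does not mention 146. It also says that a detailed sample size calculation is not yet possible, and adds: "We anticipate adding this to the protocol after inclusion of the study population has been completed". It leaves room to enlarge the trial: "If the sample size after one year is estimated to be too small, additional patients will be included".

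**The concern.** There are two problems. First, enrolled patients cannot be fewer than randomised patients, yet the timeline completes enrolment at 126 while the sample size section needs up to 146 randomised. Second, the step from 37 per group to 146 in total does not fit the loss rate given in the same sentence. An allowance for loss has to leave the required number after the loss, so the evaluable number is divided by (1 - loss). The total of 146 is too small for that.

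The 90% power is the stated basis for the primary comparison. If the randomised number does not deliver it, the chance of missing the assumed 10-point effect is higher than the plan tells its readers. A reader also cannot tell from the text which total governs recruitment.

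**Working it through.** **Inputs.** From *Study endpoints and sample size calculation*: difference 10 points, common SD 13, two-sided alpha 0.05, power 90%, 37 per group, loss 30-35%, total up to 146. From *Research Design*: three arms, 1:1:1. From *Publication Strategy/Additional Information*: total 126, at 5-6 a month for 24 months.

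**Step 1: reproduce the 37.** For a two-sample comparison of means, the normal approximation is n = 2(z₀.₉₇₅ + z₀.₉₀)² × (SD/difference)² = 2 × (1.960 + 1.282)² × (13/10)² ≈ 35.5, rounded up to 36. The t-test (noncentral t) gives 36.50, rounded up to 37. Power by t-test is 89.6% at 36 and 90.4% at 37. The plan's 37 is correct, and three arms need 3 × 37 = 111 evaluable patients.

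**Step 2: total needed at the stated loss.** N = 111/(1 - loss).
- 30%: 111/0.70 = 158.6, so 159 (53 per arm)
- 35%: 111/0.65 = 170.8, so 171 (57 per arm)

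Starting from 36 per arm does not rescue 146: 108/0.70 = 154.3 and 108/0.65 = 166.2.

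**Step 3: where 146 could come from.** The plan does not show its working. Multiplying by (1 + loss) gives 111 × 1.30 = 144.3 to 111 × 1.35 = 149.9, or 108 × 1.35 = 145.8. So 146 is consistent with multiplying where division was needed, but this is an inference, and the shortfall is the same however 146 was reached. Neither method gives 126 at 30-35% loss.

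**Step 4: loss each total can absorb.** Largest loss = 1 - 111/N.
- 146: 1 - 111/146 = 24.0%
- 126: 1 - 111/126 = 11.9%

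Both are below the plan's 30-35%.

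**Step 5: what remains, and the power.** Evaluable per arm = N × (1 - loss)/3, kept fractional. Power is by t-test with difference 10 and SD 13. The last column is the difference for which 90% power would hold.

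| Total | Loss | Evaluable per arm | Power | Type II error | Difference with 90% power |
|---|---|---|---|---|---|
| 146 | 30% | 34.07 | 87.9% | 12.1% | 10.36 |
| 146 | 35% | 31.63 | 85.3% | 14.7% | 10.77 |
| 126 | 30% | 29.40 | 82.6% | 17.4% | 11.18 |
| 126 | 35% | 27.30 | 79.7% | 20.3% | 11.62 |

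**Step 6: accrual.** 5 × 24 = 120 and 6 × 24 = 144. The figure of 126 (126/24 = 5.25 a month) lies inside that range. The figure of 146 (146/24 = 6.08 a month) lies just outside it. The timeline is therefore built on the smaller total.

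**The case against.** The arithmetic is not in dispute; the objections concern its weight.

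- **The shortfall at 146 is small.** It costs 2-5 points of power, and the SD and effect are themselves borrowed from patients on clopidogrel. This stands: taken alone, the 146 shortfall is modest.
- **126 may be only an accrual forecast.** It sits in a timeline paragraph with no power claim attached, and the 146 is worded as an upper limit. This stands in part, since only the sample size section states a requirement. But the timeline calls 126 the total at which enrolment is complete, and the upper limit is tied to the 30-35% loss, for which even 146 is too few. The figure of 126 would suffice only at about 12% loss, which the plan nowhere assumes.
- **Patients can be added after one year.** This means 126 is not a fixed stop. But no criterion, target or maximum is given, and the detailed calculation is deferred until inclusion is complete. The provision cannot support a 90% claim and does not say which total applies.
- **Covariate adjustment could recover power.** The *Statistical analysis plan* uses ANCOVA, but only with baseline variables that differ significantly between groups. The gain is not assured, and the sample size calculation takes no credit for it.

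**Conclusion.** The concern holds. The two totals contradict each other, and at the plan's own loss rate neither delivers the stated 90% power. With 146 the power is 85-88%, a modest shortfall. With 126 it is 80-83%, so the type II error is 1.7 to 2.0 times the stated 10%. The base figure of 37 per group is right; the faults lie in the inflation step and in the unreconciled 126.

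These figures assume the plan's difference and SD, equal arms, equal loss across arms, and an unadjusted two-sample t-test. The inflation error does not affect the type I error or the choice of endpoint. This is a must-fix item because the trial's size and its power are basic design facts, and the text as written gets the power wrong and leaves the size unclear.

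**What to change.** Use one total in both sections, derive the loss allowance as n/(1 - loss), and state the power that the chosen total gives.

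- **If 146 is kept:** state that up to 146 patients are randomised, that about 32-34 evaluable patients per group remain after 30-35% loss, and that power is about 85-88%. Change the 126 to 146 and align the accrual statement: 146 takes 24.3 months at 6 a month and 29.2 months at 5 a month.
- **If 126 is kept:** state about 27-29 evaluable per group and about 80-83% power, and replace the 146.
- **If 90% power is to be kept:** the total must be 159 (30% loss) to 171 (35% loss). That is 13-25 more patients than 146, or 33-45 more than 126.

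It would also help to say that the power statement does not rely on the one-year provision to add patients, or else to give that provision a criterion and a maximum.

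Either of the first two options is a wording change with no added visits or assays per patient and no total above those already in the plan, though choosing 146 means 20 more patients than the timeline now shows. The cost is a less favourable power statement: about 2-5 points lower for 146, about 7-10 points lower for 126.

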vorapaxar 2.5mg od; 2) prasugrel/ticagrelor plus vorapaxar 2.5mg od; 3) continue DAPT with aspirin and prasugrel/ticagrelor. Randomized treatment will be administered for 30 ± 3 days; prasugrel and ticagrelor will be administered at their standard maintenance dose (10mg od and 90mg bid, respectively). Randomization will be stratified according to type of P2Y₁₂ inhibitor, in order to include at least 35% of patients on prasugrel. The rationale for predicting a higher number of randomized patients on ticagrelor derives from the more broad clinical indications of ticagrelor compared with prasugrel. Patient who entered the study before being on DAPT for 2 weeks will be required to complete 2 weeks of DAPT with aspirin and prasugrel/ticagrelor before randomization.

Blood sampling for PD testing will be conducted at 3 time-points: a) baseline (while patients will be on standard DAPT prior to initiating randomized treatment); b) after 7-10 days of randomized study treatment; c) after 30 ± 3 days of randomized study treatment. At each time point, blood will be collected before the morning dose of prasugrel/ticagrelor and vorapaxar, in order to measure trough levels of platelet inhibition. During study treatment in-hospital major adverse cardiac events (death, MI, stroke, and urgent revascularization procedures) and serious adverse events (bleeding and other adverse events) will be collected. Bleeding will be defined by the BARC (Bleeding Academic Research Consortium) definition [19].

After study completion, patients will resume antiplatelet treatment regimen at the discretion of the treating physician. A flow diagram of the study design is illustrated below.

Laboratory assessments

Peripheral venous blood samples (20 mL) will be drawn through a short venous catheter inserted into a forearm vein and collected in citrate, EDTA, and serum tubes as appropriate for assessments. The first 2-4 mL of blood will be discarded to avoid spontaneous platelet activation. Blood sampling for PD will be performed at 3 time points as indicated above in the study design section. Various PD assays will be performed as described below. Given the potential interplay between PAR-1 and P2Y₁₂ mediated signaling, assessments specific for both pathways will be conducted [11]:

1. Light transmittance aggregometry (LTA)
2. Thrombelastograph Coagulation Analyzer TEG 6s Series system (CORA[®] system)
3. Whole blood vasodilator-stimulated phosphoprotein (VASP)
4. Serum thromboxane B2

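### The primary day-30 analysis discards every patient without a valid day-30 sample and makes no use of their day 7-10 value; at 146 randomised its power is about 85-88%, not 90%

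*Combined protocol and SAP*

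**What the plan says.** The section on study endpoints and sample size defines the primary endpoint as the "comparison of CAT-induced MPA between DAPT and DAPT plus vorapaxar after 30 ± 3 days of treatment". The calculation reads "Assuming a 10% absolute reduction in CAT-induced MPA" "with a common standard deviation of 13"%, "with a 90% power and 2-sided" alpha of 0.05, and arrives at 37 patients per group. It then allows for a possible "30-35% rate of invalid results due to hemolysis or drop-out" and sets the number to randomise over three arms at up to 146. The rate is not divided between its two causes.

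Research Design schedules PD sampling at baseline, "b) after 7-10 days of randomized study treatment", and at 30 ± 3 days. The middle sample is used only under the other objectives, which compare the groups at each time point and look at change within groups.

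The Statistical analysis plan lists Student's t, Mann-Whitney and Wilcoxon tests. It adds "An analysis of covariance (ANCOVA) method with a general linear model", whose covariates are whichever baseline variables differ significantly between groups, and ANOVA for intragroup comparisons. The significance rule is "A 2-tailed p value of < 0.05 is considered to indicate a statistically significant difference". No analysis set, missing-data assumption, mixed model or sensitivity analysis is named.

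**The concern.** A t test, Mann-Whitney test or ANCOVA of the day-30 value can only use patients who have one. That the primary analysis is a complete-case analysis is therefore an inference from the named methods and from the plan's silence on missing data. On the plan's own allowance, up to about a third of randomised patients could be left out, including some whose response to randomised treatment was already measured at day 7-10.

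Two things are at stake. The first is precision: the number of valid day-30 samples may be too small for the stated power, while related data already collected go unused. The second is comparability. Hemolysis, in samples tested by a blinded laboratory, is plausibly unrelated to arm. Drop-out may not be: treatment is open label, two arms add vorapaxar, one of them also stops aspirin, and the protocol names bleeding as vorapaxar's most important adverse effect. A larger sample does not correct selective loss, and a single pooled rate does not show how much of the loss is of that kind.

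**Working it through.** **Inputs from the protocol.** Difference 10 points, SD 13 points, two-sided alpha 0.05, power 90%, 37 per group, loss 30-35%, 146 randomised 1:1:1 (146/3 = 48.67 per arm).

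**1. The plan's 37 per group.** Normal approximation: n = 2 × (1.960 + 1.282)² × 13² / 10² = 35.5, so 36. With the exact noncentral t, power is 89.6% at 36 and 90.4% at 37. The 37 reproduces.

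**2. Where 146 comes from.** Evaluable patients needed: 3 × 37 = 111.
- Multiplying by (1 + loss): 111 × 1.30 = 144.3, so 145; 111 × 1.35 = 149.85, so 150. The ratio 146/111 = 1.315 lies in this range, and 3 × 36 × 1.35 = 145.8 also rounds up to 146.
- Dividing by (1 − loss): 111/0.70 = 158.6, so 159; 111/0.65 = 170.8, so 171.
- The loss that 146 actually covers: 1 − 111/146 = 24%.

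**3. Power of the day-30 complete-case t test.**

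| Randomised | Loss | Valid per arm | Power |
|---|---|---|---|
| 146 | 30% | 48.67 × 0.70 = 34.1 | 87.9% |
| 146 | 35% | 48.67 × 0.65 = 31.6 | 85.3% |
| 159 | 30% | 53 × 0.70 = 37.1 | 90.5% |
| 171 | 35% | 57 × 0.65 = 37.05 | 90.4% |

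**4. What the day 7-10 value could add.** Let n be the valid day-30 samples per arm, m the patients per arm with a valid day 7-10 sample but no day-30 sample, and ρ the correlation between the two visits. The variance of the day-30 arm mean is multiplied by 1 − ρ² × m/(n + m). The documents give neither ρ nor the share q of lost patients who have a day 7-10 value, so both are assumptions. At 35% loss, n = 31.6 and m = 17.03 × q:

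| ρ | q | Variance factor | Effective n per arm | Power |
|---|---|---|---|---|
| 0.3 | 0.25 | 0.989 | 32.0 | 86% |
| 0.5 | 0.50 | 0.947 | 33.4 | 87% |
| 0.7 | 0.50 | 0.896 | 35.3 | 89% |
| 0.7 | 0.75 | 0.859 | 36.8 | 90% |
| 0.7 | 1.00 | 0.829 | 38.2 | 91% |
| 0.8 | 1.00 | 0.776 | 40.8 | 93% |

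At 30% loss the same grid runs from 88% to 94%. The gain at 35% loss is therefore between about 0.4 and 8 points of power. It is nil for patients lost before day 7-10. Any gain from adjusting for baseline CAT-MPA comes on top and cannot be quantified from the documents.

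**5. Size of a drop-out bias.** If a share g of one arm is lost selectively and those patients would have differed by k points from the patients who remain, the arm mean is off by g × k.
- The only documented rates to set against g are those under Possible Discomforts and Risk: TIMI clinically significant bleeding of 15.8% on vorapaxar and 11.1% on placebo, which the protocol attributes to a long-term (3-year) trial. At a constant hazard (an assumption), the 30-day risk is 1 − (1 − 0.158)^(30/1095) = 0.47% and 1 − (1 − 0.111)^(30/1095) = 0.32%.
- With g = 0.0047 and an assumed k of 10, the bias is about 0.05 points, against the planned effect of 10.
- With g = 0.10 and k = 5 it would be 0.5 points, and with g = 0.35 and k = 5 it would be 1.75 points. These last two are illustrations; no figure in the documents supports either.

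**The case against.** The strongest reply is that the power shortfall is an inflation error and not an analysis error. That stands. With 159 or 171 randomised, the planned complete-case test reaches 90%, and the protocol also allows patients to be added if the sample is judged too small after one year. The mixed model is thus an efficient use of data already collected, not the only route to 90% power.

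A reader might infer that the mixed model restores 90%. The documents do not support that. The upper end of the range needs every lost patient to have a valid day 7-10 sample. If hemolysis affects each visit at a similar rate, the share is nearer 65-70%. At a share of 0.65 and 35% loss, power is 87.6% for correlation 0.5 and 89.8% for 0.7.

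A reader might also infer that bleeding-related drop-out seriously distorts the primary result. On the protocol's own rates it may be very small over 30 days, and patients at increased bleeding risk are excluded. Early or minor bleeding could raise it, but nothing in the documents supports a figure near 10%. If patients with the strongest inhibition left the vorapaxar arm, the effect would be understated, not exaggerated.

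Two matters of wording also count. The plan calls the loss possible, not expected, and does not tie it to the day-30 sample alone. Nor are the day 7-10 data ignored throughout the plan: they are compared separately, and are absent only from the primary test.

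Finally, a mixed model assumes that loss is explained by observed values. It does not correct drop-out that depends on the unseen day-30 result. That also stands, and is why a sensitivity analysis is needed beside it.

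**Conclusion.** The point holds in a limited form. If the loss the plan allows for occurs, the named day-30 analyses have 87.9% to 85.3% power at 146 randomised, 2 to 5 points below the stated 90%. This follows from the plan's own difference, SD and loss rate. It rests on reading the named tests as complete-case analyses and applying the loss rate to the day-30 sample. The cause is the inflation formula.

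Using the day 7-10 value would recover part of the shortfall or all of it, depending on a visit correlation and a share of usable samples that the documents do not give: about 86% to 93% at 35% loss. Bias from drop-out cannot be excluded in an open-label comparison, but its size is unknown and the documents do not show it to be material. The mixed model is a worthwhile low-cost improvement and not a repair without which the trial fails.

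The enrolment plan gives a total of 126 instead of 146. At 126 the same test would have 82.6% power at 30% loss and 79.7% at 35%. The two totals need to be reconciled as a separate matter.

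**What to change.** 1. Restate the power at 146 randomised as about 85-88% for 30-35% loss, or recalculate the number to randomise by dividing by (1 − loss).
2. Make the primary analysis a linear mixed model of CAT-MPA at day 7-10 and day 30. Include all randomised patients with at least one valid post-baseline sample, in their assigned arm. Use arm, visit, arm-by-visit, baseline CAT-MPA and P2Y12 inhibitor stratum as fixed effects, with an unstructured covariance. The day-30 contrast of DAPT plus vorapaxar against DAPT is the primary result.
3. Report losses from hemolysis and from drop-out separately by arm.
4. Add one sensitivity analysis that shifts imputed day-30 values over a stated range for drop-outs only, not for hemolysed samples.

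The cost of items 2 to 4 is SAP wording and a little more analysis, with no added visits or samples; the planned SPSS v22 can fit the model. Recalculating the sample size in item 1 would mean randomising 159 to 171 patients, whereas restating the power costs nothing. The downside of item 2 is that the primary result then rests on a missing-at-random assumption, which item 4 probes.

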This may indeed represent a limitation for the uptake of vorapaxar in modern day clinical practice where these agents are being more broadly utilized [1,2]. This knowledge gap represents an important area for exploratory research as it represents how vorapaxar could potentially be used in daily clinical practice. Further, given the potent and comprehensive antiplatelet effects achieved with the novel P2Y₁₂ receptor inhibitors, the role of aspirin when added to these agents have been questioned [16,17]. Prasugrel and ticagrelor are effective in inhibiting both ADP P2Y₁₂-dependent and thromboxane A₂-dependent pathways of platelet aggregation [16,17]. In particular, the platelet inhibition achieved by combining aspirin and a potent P2Y₁₂-receptor blocker was shown to be no greater than that produced by the P2Y₁₂-receptor blocker alone in healthy volunteers [16,17]. Therefore, the role of vorapaxar as part of a dual antithrombotic treatment regimen including prasugrel or ticagrelor and stopping aspirin, represents another important area of clinical interest as it has the potential to maximize ischemic protection while reducing the risk of bleeding.

Study Aims

To assess the pharmacodynamic effects of vorapaxar in addition to antiplatelet therapy with a novel P2Y₁₂ receptor inhibitor (prasugrel or ticagrelor) with and without aspirin in a real-world setting of post-MI patients. Exploratory assessments on the safety will also be evaluated.

Research Plan

Study Population

Inclusion criteria:

1. Patients with a prior MI within the previous 12 months.

2. On DAPT with low-dose aspirin (81mg od) and either prasugrel (10mg od) or ticagrelor (90mg bid) as per standard-of-care.
3. Free from bleeding and ischemic events after the index MI event.
4. Age between 18 and 75 years old.

Exclusion criteria:

1. History of stroke, transient ischemic attack, or intracranial hemorrhage.
2. Active pathological bleeding, history of bleeding events or increased risk of bleeding.
3. Known severe hepatic impairment.
4. Age >75 years.
5. Body weight <60 Kg.
6. Use of strong CYP3A inhibitors (e.g., ketoconazole, itraconazole, posaconazole, clarithromycin, nefazodone, ritonavir, saquinavir, nelfinavir, indinavir, boceprevir, telaprevir, telithromycin and conivaptan) or inducers (e.g., rifampin, carbamazepine, St. John's Wort and phenytoin).
7. On treatment with any oral anticoagulant (vitamin K antagonists, dabigatran, rivaroxaban, apixaban, edoxaban).

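### The only result that can fulfil the secondary hypothesis on stopping aspirin is a non-significant p value, which a true rise of up to about 6 points in CAT-induced MPA would give at least half the time

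*Combined protocol and SAP*

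**What the plan says.** Under *Study endpoints and sample size calculation*, one secondary outcome is named. It begins "Our secondary outcome will be the comparison of CAT-induced MPA between vorapaxar in addition to a new generation" P2Y₁₂ inhibitor, and the comparator is vorapaxar on top of aspirin plus that inhibitor. The hypothesis attached to it is "We hypothesize that stopping aspirin will not lead to significant differences in CAT-induced MPA after 30 ± 3 days of treatment".

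The *Statistical analysis plan* lists difference tests only (t test, Mann-Whitney, Wilcoxon, ANCOVA, ANOVA) and gives one criterion: "A 2-tailed p value of < 0.05 is considered to indicate a statistically significant difference for all the analyses performed".

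The sample size rests on the primary comparison alone: "Assuming a 10% absolute reduction in CAT-induced MPA with a common standard deviation of 13" percent, from which "37 patients per group will be needed to detect a significant difference between DAPT and DAPT plus vorapaxar". Neither section gives a margin, a confidence-interval rule or a power figure for the aspirin-free comparison.

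*Publication Strategy/Additional Information* adds that "variability may be higher than expected and we cannot currently perform a detailed sample size calculation". *Study Rationale* gives the "role of vorapaxar as part of a dual antithrombotic treatment regimen including prasugrel or ticagrelor and stopping aspirin" as an area of clinical interest that motivates the study.

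**The concern.** A hypothesis of no significant difference, judged by a test for a difference, is fulfilled when the test fails to reject. Failure to reject can mean that the arms are alike, or that the data are too few or too noisy to separate them. For any true non-zero difference, lost samples and higher variability both make the hypothesised result more likely. The plan expects 30-35% invalid or lost results and itself warns about variability.

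The documents do not say that p ≥ 0.05 will be reported as equality. But they name no other result that would fulfil the hypothesis.

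At stake is the interpretation of the one named secondary outcome. One of the three arms exists to study vorapaxar without aspirin. A non-significant result would fit the hypothesis as worded even if the data could not exclude a rise as large as the whole effect assumed for adding vorapaxar.

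**Working it through.** **Inputs from the documents.** Difference 10 points, SD 13 points, 90% power, two-sided α 0.05, 37 evaluable per group, 30-35% lost or invalid, 1:1:1 allocation, up to 146 randomized (sample-size section), 126 enrolled (timeline).

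**Assumption.** The SD of 13 also holds for the secondary comparison; the plan states it for the primary one only.

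**The plan's own figure.** The exact two-sample t test with a difference of 10 and SD 13 has power 0.896 at 36 per group and 0.904 at 37. The stated 37 is reproduced.

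**Evaluable patients per arm.**
- 146/3 × 0.70 = 34.1 and 146/3 × 0.65 = 31.6, so 34 down to 31.
- 126/3 × 0.70 = 29.4 and 126/3 × 0.65 = 27.3, so 29 down to 27.

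**Precision.** SE = 13 × √(2/n), and half-width = t(0.975, 2n−2) × SE. At n = 37, SE = 13 × √(2/37) = 3.02 and the half-width is 1.993 × 3.02 = 6.03. An observed rise just short of significance is about one half-width above zero, so its upper 95% limit is about 2 × half-width. Probabilities of a non-significant result come from the noncentral t.

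| Evaluable per arm | Half-width | Upper limit, rise just non-significant | True rise missed half the time | 5-point rise non-significant | 10-point rise non-significant |
|---|---|---|---|---|---|
| 37 | 6.03 | 12.05 | 6.00 | 62.8% | 9.6% |
| 34 | 6.30 | 12.59 | 6.27 | 65.4% | 12.2% |
| 31 | 6.60 | 13.21 | 6.58 | 68.1% | 15.4% |
| 29 | 6.84 | 13.68 | 6.81 | 69.8% | 17.9% |
| 27 | 7.10 | 14.20 | 7.06 | 71.6% | 20.8% |

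The 5-point rise is an illustration; the documents name no loss of inhibition that would matter.

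**If the SD differs.** At SD 10, a 5-point rise is non-significant 43.6% of the time (37 per arm) to 56.2% (27 per arm). At SD 16 the figures are 73.6% and 79.7%.

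**If a margin were used.** With an illustrative margin of 5 points, one-sided α 0.025, true difference zero and SD 13, power is 37.2% at 37 per arm and 28.3% at 27. Reaching 80% needs 108 evaluable per arm, and 90% needs 144.

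**The case against.** The strongest reply is that the harm is inferred. The sentence states an expectation, and no section says that a non-significant result will be presented as equivalence or used to support dropping aspirin. This is also a pharmacodynamic study that appeals to recommendations for pilot work. It is true that misuse is not announced. But the hypothesis still has no other way to be fulfilled, and a pilot purpose favours estimation with intervals over a non-significant test.

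Further points can be made:

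- **Large losses would usually be detected.** This stands: at 37 per arm the comparison has about 90% power for 10 points. For the interval to reach 10 points while p stays non-significant, the observed rise must be about 4.0 to 6.0. By normal approximation that happens about 7% of the time if the true difference is zero and 27% if it is 5 points (18% and 45% at 27 per arm). The weakness concerns intermediate losses.
- **Other comparisons cover the aspirin-free arm.** The plan also compares all three groups on every parameter at each time point. These too are difference tests without a margin.
- **The planned model is ANCOVA, and the working uses a t test.** With baseline MPA as a covariate and an assumed correlation of 0.5, the half-width at 37 per arm falls to 6.03 × √0.75 = 5.2. The plan does not guarantee that covariate, because only baseline variables that differ significantly enter, and 5.2 does not change the conclusion.
- **The smallest sizes combine the 126 forecast with full losses, and patients may be added.** That is fair, but the provision to add patients sets no precision target for this comparison. The point already holds at 37.

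**Conclusion.** The concern holds. The hypothesis is worded so that only failure to find a difference can fulfil it, and at the planned size such a failure says little about losses below about 6 points at 37 evaluable per arm, or about 7 at 27. It is reasonable, though not conclusive, evidence against a 10-point loss.

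The absence of a margin, interval rule and power is plain from the text. The sizes depend on carrying the SD of 13 over to this comparison and on an unadjusted analysis. The primary comparison is not affected. This should be fixed: it concerns a secondary outcome, but the stated criterion cannot support the conclusion it invites.

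**What to change.** In the endpoint section and the SAP:

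1. Make the secondary comparison an estimate: the 30-day difference in CAT-induced MPA (vorapaxar plus P2Y₁₂ inhibitor minus vorapaxar plus DAPT) with its two-sided 95% CI, from the model used for the other between-group comparisons.
2. State that p ≥ 0.05 will not be read as no difference.
3. Reword the hypothesis to match, for example: we will estimate the change in CAT-induced MPA when aspirin is stopped.
4. Allow a claim of not being materially worse only if the upper 95% limit lies below a margin justified and recorded before the data are seen. The 10-point figure is the whole effect assumed for vorapaxar and should not become that margin by default.

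Because a margin as tight as 5 points would need about 108 to 144 evaluable per arm, estimation is the realistic choice at the planned size.

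The cost is two or three sentences, with no extra patients or assays. The drawback is that a no-difference claim becomes harder to make, and the result will probably be reported as inconclusive about small losses.
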